6.5.7 Visit 7: Week 10 (± 2 days)

Follow-Up Visit

- Vital Signs
- BSCVA (Snellen's chart)
- OSDI
- Clinical Global Impression, Subject Global Assessment
- Ophthalmic Examination (slit lamp examination, Ocular surface redness score)
- Physical Inspection of the Nose and Oropharynx
- Record changes in concomitant medication and adverse events.

7 Statistical Plan

7.1 Sample Size Determination

The sample size is based on the primary efficacy end point (corneal RBS score) using the following assumptions: (i) mean RBS score in ocular GVHD population = 3.1, (ii) sigma (standard deviation) = 2.5, (iii) expected mean based on 60% effect = 1.24. These assumptions are based on our preliminary data in ocular GVHD patients where we found that treatment with DNase I eye drops reduced RBS score by 80% (mean).²⁵ A total of 30 subjects in each group will be required to detect the difference between groups using a 2-sided two-sample t test with an alpha level of 0.05 and 80% power. We elected to enroll 36 subjects per group.

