	8.5.		
	8.6	ADVERSE EVENT REPORTING	
	8.6.		
	8.6.		
	8.6.	-	
	0.0.	8.6.3.1 FOLLOW-UP INFORMATION	
	8.7	STUDY CLOSE-OUT	
	8.7		
	0.7	8.7.1.1 7 CALENDER DAY TELEPHONE OR FAX REPORT.	
		8.7.1.2 15 CALENDER DAY WRITTEN REPORT	
	8.8	FAX NUMBER FOR IND SAFETY REPORTS.	
	8.9	IN CASE OF EMERGENCY	
	8.10	DATA SAFETY MANAGEMENT PLAN	
	8.11	STUDY OVERSIGHT	_
	8.12	REPORTING CHANGES IN STUDY STATUS	
9	DAT	A QUALITY AND SAFETY REVIEW PLAN AND MONITORING	39
	9.1	DATA QUALITY AND MANAGEMENT	39
	9.1	-	
	9.1		
	9.2	SUBJECT ACCRUAL AND COMPLIANCE	
	9.2		

	9.2	2.2 MEASUREMENT AND REPORTING OF PARTICIPANT ADHERENCE TO TREATMENT PROTOCOL	40
g	9.3	STOPPING RULE	40
	9.4	DATA AND SAFETY MONITORING BOARD (DSMB)	40
	9.4		
9	. 5	SAFETY REVIEW PLAN	41
10	CON	NFIDENTIALITY	41
11	sou	JRCE DOCUMENTS	42
1	1.1	RECORDS RETENTION	42
12	ETH	ICAL CONSIDERATIONS	42
13	STU	DY FINANCES	
1	3.1	FUNDING SOURCE CONFLICT OF INTEREST	43
1	3.2	CONFLICT OF INTEREST.	43
1	3.3	SUBJECT STIPENDS OR PAYMENTS	43
14	REF	ERENCES	44
15	APP	ENDIX I	47

SCHEDULE OF VISITS AND PROCEDURES

	gı	(e)	(es)					
	Screening	Day 1 (Pre-Dose)	Day 1 (Post-Dose)	Week 2	Week 4	Week 6	Week 8	Week 10
Informed consent	Х							
Demographic information	Χ							
Medical history/ Con Meds/ Transplant history	Х							
Ophthalmic/ oGVHD history	Χ							
Vital signs		Х		Χ	Χ	X	Χ	Х
Best Spectacle Corrected Visual Acuity		Х						Х
Ocular Surface Disease Index (OSDI)	X	Х		Χ	Χ	X	Χ	Х
Clinical Global Impression (CGI)				Χ	Χ	Х	Χ	Х
Subject Global Assessment (SGA)				Χ	Χ	Χ	Χ	Х
Visual Analogue Scale (VAS)			Х	Х	Х	Х	Х	
Ophthalmic examination (Slit lamp)	Χ	Х		Χ	Χ	Х	Χ	Х
Schirmer 1 test and Fluorescein and Lissamine Dye staining	Х	Х					Х	
Ocular surface Redness (OR) score		Х		Χ	Χ	Χ	Χ	Х
Tear fluid analysis (PicoGreen, Cellometry)		Х					Χ	
Keratograph Oculus Redness Score		Χ			Χ		Χ	
Non-invasive Keratography Tear Film Break-up Time (NIKBUT)		Х			Χ		Χ	
Tear Meniscus Height (TMH)		Χ			Χ		Χ	
TearLab Osmolarity Test		Х			Χ		Χ	
InflammaDry for MMP-9 Protein		Х			Х		Х	
Pregnancy test (urine)*	Х							
Randomization visit		Х						
First study medication		Х						
Drug dispensation visits			Х	Х	Х	Х		
Instruction on study medication self- administration			Х	Х	Х	Х		

Version: 10.0; 07-26-2018

Physical inspection of nose & oropharynx	Х		Х	Х	Х	Х	Х
Adverse Events/ Concomitant Medications	Х	X++	Х	Х	Х	Х	Х
Conjunctival culture**	Х					Х	

^{*}If applicable ++ AEs only

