ABBREVIATIONS

ADR Adverse Drug Reaction

AE Adverse Event

APC Antigen-presenting cells

BSCVA Best Spectacle Corrected Visual Acuity

EC Ethics Committee eDNA Extracellular DNA

CNL Corneal Neurobiology Laboratory

CRF Case Report Form

CGI Clinical Global Impression
DCF Data Clarification Form
DNase I Deoxyribonuclease I

FDA Food and Drug Administration

FVC Forced vital capacity
GCP Good Clinical Practice

ICH International Conference on Harmonization

IB Investigator's Brochure
 IOP Intraocular pressure
 IRB Institutional Review Board
 KCS Keratoconjunctivitis sicca
 Net Neutrophil extracellular trap

NIKBUT Non-invasive Keratograph Tear Film Break-Up Time

oGVHD Ocular Graft-Vs.-Host Disease
OSDI Ocular Surface Disease Index

Otc Over the counter QID Four times per day

rhDNase I Recombinant human deoxyribonuclease I

SAE Serious Adverse Event SGA Subject Global Assessment

SP Substance P

TMH Tear Meniscus Height

UIC University of Illinois at Chicago

VA Visual Acuity

VAS Visual Analog Scale

^{**}For select subjects only

Study Summary

Title	A Phase I/II Randomized Placebo-Controlled, Double-Blind Single-Center, tolerability and preliminary efficacy clinical trial of recombinant human deoxyribonuclease (rhDNase) eye drops in patients with ocular graft-vshost disease (oGVHD)
Short Title	RhDNase treatment for ocular GVHD
Protocol Number	UIC-CNBL-1002
Phase	Phase I/II
Methodology	Double-blind
Study Duration	10 weeks
Study Center(s)	Single-center
Objectives	To evaluate the tolerability and preliminary efficacy of rhDNase I eye drops in patients with ocular graft-vshost disease (oGVHD).
Number of Subjects	72 (study drug- 36, placebo- 36)
Diagnosis and Main Inclusion Criteria	Men and women ≥ 18 years of age with a diagnosis of oGVHD, with Schirmer I <10, Ocular surface staining ≥1 and OSDI mild (≥13).
Study Product, Dose, Route, Regimen	Study drug: rhDNase I (Pulmozyme®), 0.1% eye drops four times a day for eight weeks. Control: Vehicle eye drops four times a day for eight weeks.
Duration of administration	8 weeks
Reference therapy	Vehicle eye drops four times a day for eight weeks.

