Statistical Methodology	One eye (target eye) will be selected at screening visit for statistical comparisons as follows: (i) if only 1 eye meets inclusion criteria, this eye is used; (ii) if both eyes meet inclusion criteria, the eye with the higher RBS score is used; (iii) if both eyes have the same RBS score, then the one with the lower Schirmer I score is used; (iv) if both eyes have same scores, the right eye is used. Secondary analyses will be performed for the non-target eye as well. To assess the effect of treatment, we will compare each outcome measure between rhDNase I (study) vs. Vehicle group over time using general linear mixed model, mixed-effects ordinal logistic regression, and mixed-effects multinomial logistic regression for continuous, ordinal and nominal variables respectively. Treatment, time and their interaction will be included in the model. Missing values of less than 25% will be imputed by using multiple imputations; otherwise will not be included in the analysis. Descriptive statistics will be utilized before the modeling to describe the sample. Assumptions behind each statistical method will be examined. Two-sided P -value less than 0.05 would be considered as statistical significance. All the analyses will be conducted by using SAS 9.2 (SAS Inst., Cary, NC).

1 Introduction

This document is a protocol for a human research study. This study is to be conducted according to US and international standards of Good Clinical Practice (FDA Title 21 part 312 and International Conference on Harmonization guidelines), applicable government regulations and Institutional research policies and procedures.

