3.3.1 Efficacy End Point: Ocular surface Fluorescein and Lissamine Dye staining score

[figure not shown]
Ocular surface staining will be assessed using Fluorescein dye for Cornea and Lissamine Green Dye for conjunctiva. The scoring pattern is represented below.

Fluorescein Dye for Cornea:

Using the insulin syringe, 2 units (20uL) of the 1ml insulin syringe will be drawn out from the fluorescein bottle and fluorescein in the syringe will be released into sterile 1ml Eppendorf vial and capped. Using 5µL fixed pipette and a 10µL pipette tip 5µL of the fluorescein will be drawn from the Eppendorf vial and after slightly pulling down the right lower eye lid of the patient fluorescein will be released into the lower conjunctival sac. After waiting for 30 seconds the process will be repeated in the left eye. Recording of corneal fluorescein staining will be performed by a slit lamp examination after 2 minutes and 30

[figure not shown]
seconds for each eye using the grading system described below. Corneal staining will be graded in 5 zones

Each zone will be graded from 0 to 3 based on the density of punctate staining.

Lissamine Green Dye for Conjunctiva:

Using the insulin syringe, 2 units (20uL) of the 1ml insulin syringe will be drawn out from the Lissamine bottle and Lissamine in the syringe will be released into sterile 1ml Eppendorf vial and capped. Using 5uL fixed pipette and a 10uL pipette tip 5uL of the Lissamine will be drawn from the Eppendorf vial and after slightly pulling down the right lower eye lid of the patient Lissamine will be released into the lower conjunctival sac. After waiting for 30 seconds the process will be repeated in the left eye. Using the slit lamp (white light of moderate intensity) nasal-bulbar and temporal-bulbar conjunctiva will be graded within 2 minutes for each eye.

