4.1 Inclusion Criteria

The PI and other members of International Chronic Ocular GVHD Consensus Group have established the consensus diagnostic criteria and classification for chronic ocular GVHD.⁴⁰

Table 1: Severity scale in chronic ocular GVHD

Severity scores (points)	Schirmer's test (mm)	CFS (points)	OSDI (points)	Conj (points)
0	>15	0	<13	None
1	11–15	<2	13–22	Mild/Moderate

Severity scores (points)	Schirmer's test (mm)	CFS (points)	OSDI (points)	Conj (points)
2	6–10	2–3	23–32	Severe
3	≤5	≥4	≥33	

CFS; corneal fluorescein staining, OSDI; Ocular Surface Disease Index. Conj; conjunctival injection. Severity classification; Total score (points); (Schirmer's test score+ CFS score+ OSDI score+ Conj injection score) = None;0–4, Mild/Moderate; 5–8, Severe, 9–11.

Table 2: Diagnosis of chronic ocular GVHD

	None (points)	Probable GVHD (points)	Definite GVHD (points)
Systemic GVHD(-)	0–5	6–7	≥8
Systemic GVHD(+)	0–3	4–5	≥6

Based on these criteria (Tables 1 and 2),⁴⁰ patients with definite ocular GVHD will be enrolled. Additionally, all of the following criteria should be met to be eligible for the study:

- Aged 18 years or older.
- Capable of giving informed consent and does provide informed consent.
- Schirmer I <10
- Corneal/ conjunctival (Fluorescein and Lissamine Dye) staining ≥1
- Ocular symptoms must be considered as annoying or activity limiting (OSDI ≥13; mild).
- Women must be post-menopausal ≥ 1 year, or surgically sterilized. If not, a negative urine pregnancy test is required within 14 days of receiving her first dose of test medication (placebo/ study drug) along with definite evidence of contraceptive use during the duration of the study. Women of reproductive age should use a method of birth control that is acceptable to the subject and the study doctor. This may include oral contraceptive pills, birth control implants, barrier methods or abstinence. If a subject mentions she suspects she may be pregnant after being enrolled, another pregnancy test will be administered. If the test is positive, she will be discontinued from the study immediately.

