7.2 Statistical Methods

Biostatisticians from the Design and Analysis Core (DAC) of UIC-CCTS will perform the analysis. We will assess treatment efficacy based on the intent-to-treat principle using each participant's randomized treatment assignment to define treatment groups and outcomes. Safety variables will be analyzed with regard to treatment that participants actually received (the safety population). One eye (target eye) will be selected at screening visit for statistical comparisons as follows: (i) if only 1 eye meets inclusion criteria, this eye is used; (ii) if both eyes meet inclusion criteria, the eye with the higher RBS score is used; (iii) if both eyes have the same RBS score, then the one with the lower Schirmer I score is used; (iv) if both eyes have same scores, the right eye is used. Secondary analyses will be performed for the non-target eye as well. To assess the effect of treatment, we will compare each outcome measure between rhDNase I (study) vs. Vehicle (control) group over time using general linear mixed model, mixed-effects ordinal logistic regression, and mixed-effects multinomial logistic regression for continuous, ordinal and nominal variables respectively. Treatment, time and their interaction will be included in the model. Missing values of less than 25% will be imputed by using multiple imputations; otherwise will not be included in the analysis. Descriptive statistics will be utilized before the modeling to describe the sample. Assumptions behind each statistical method will be examined. Two-sided Pvalue less than 0.05 would be considered as statistical significance. All the analyses will be conducted by using SAS 9.2 (SAS Inst., Cary, NC).

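### The target-eye rule and the sample size use an undefined RBS score that no listed visit collects, so the eye choice is not reproducible as written and the 80% power is unsupported for corneal fluorescein staining

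*Combined protocol and SAP*

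**What the plan says.** **Where RBS is used.** Section 7.1: "The sample size is based on the primary efficacy end point (corneal RBS score) using the following assumptions". The assumptions are a mean of 3.1, an SD of 2.5 and a treated mean of 1.24 from a 60% effect. They lead to 30 subjects per group for 80% power with a two-sided two-sample t test at 0.05; 36 per group are to be enrolled.

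Section 7.2 selects one target eye at screening. If only one eye qualifies, that eye is used (step i). Step (ii): "if both eyes meet inclusion criteria, the eye with the higher RBS score is used". Step (iii), in the same words in the Study Summary: "if both eyes have the same RBS score, then the one with the lower Schirmer I score is used". Step (iv) takes the right eye if the scores are still equal.

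**What is measured.** The Schedule of Visits lists "Schirmer 1 test and Fluorescein and Lissamine Dye staining" at screening, Day 1 and week 8, and 6.5.1, 6.5.2 and 6.5.6 agree. Eligibility in 4.1 uses the same dyes: "Corneal/ conjunctival (Fluorescein and Lissamine Dye) staining ≥1". Section 3.3.1: "Ocular surface staining will be assessed using Fluorescein dye for Cornea and Lissamine Green Dye for conjunctiva". The cornea is divided into five zones: "Each zone will be graded from 0 to 3 based on the density of punctate staining". Sections 3.2 and 5.6 define the primary efficacy endpoint as corneal staining with these dyes. Section 3.3 (item 4) makes conjunctival staining a separate secondary endpoint.

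**What RBS means.** The only R entry in the abbreviation list is "rhDNase I Recombinant human deoxyribonuclease I". Section 1.4 mentions Rose Bengal staining of the cornea in a one-patient report, with the same citation that 7.1 gives, so RBS probably means Rose Bengal staining. No text makes that link.

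**The concern.** The rule that picks the eye for the primary result must run on data the trial collects. Here steps (ii) to (iv) all depend on RBS: the Schirmer and right-eye tie-breaks apply only after an RBS tie. For any subject with two eligible eyes, staff must substitute another score, and the plan does not name it. Different staff, or a later analyst, could choose differently and could not show which choice was intended.

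The second issue is power. Section 7.1 calls the corneal RBS score the primary efficacy endpoint, while 3.2, 3.3.1 and 5.6 describe a different stain and scale. If RBS is only a leftover label for corneal staining, the mean, SD and effect still need a source on the five-zone fluorescein scale. At stake is whether the stated power says anything about the endpoint the trial will analyse.

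**Working it through.** **1. Can the target-eye rule be run?**

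| Step | Needs | Collected at screening? |
|---|---|---|
| (i) one eye eligible | eligibility of each eye | yes |
| (ii) both eligible | RBS | no |
| (iii) RBS tie | RBS, then Schirmer I | RBS no, Schirmer I yes |
| (iv) still tied | RBS and Schirmer I both tied | RBS no |

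Section 7.1 attaches the word corneal to RBS, 3.2 makes corneal staining primary, and 3.3.1 assigns fluorescein to the cornea. Corneal fluorescein is therefore the natural reading, but the rule in 7.2 and the Study Summary does not say so. The documents do not state how many subjects will have two eligible eyes.

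**2. Reproducing the 7.1 figure.** Inputs from 7.1: control mean 3.1, treated mean 1.24, SD 2.5, two-sided 0.05.

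- Difference = 3.1 − 1.24 = 1.86, which is 60% of 3.1.
- d = 1.86 / 2.5 = 0.744.
- Power comes from the noncentral t distribution with 2n − 2 degrees of freedom and noncentrality d·√(n/2).
- 80% power needs n = 29.35, so 30 per arm. The plan's figure is reproduced.
- Power is 80.9% at 30 and 87.6% at 36 per arm.

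**3. Does this carry over to fluorescein?** The documents give no fluorescein mean, SD or effect, so only conditional statements are possible.

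- Detectable difference at 80% power: 0.67 SD with 36 per arm, 0.74 SD with 30.
- If the 1.86-point difference carried over, power at 36 per arm would be 97%, 88%, 74%, 60% or 49% for an assumed SD of 2.0, 2.5, 3.0, 3.5 or 4.0. It falls below 80% once the SD exceeds 1.86 / 0.67, about 2.78.
- If instead the 60% effect carried over, 80% power at 36 per arm would need a mean/SD ratio of at least 0.67 / 0.6 = 1.12. The RBS inputs have 3.1 / 2.5 = 1.24.

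**4. Vehicle response.** The inputs leave the vehicle arm at 3.1. Let v be an assumed vehicle improvement, so the vehicle mean is 3.1(1 − v). Section 7.1 does not say whether the 60% is relative to baseline (treated mean stays 1.24) or to vehicle (treated mean is 0.4 × the vehicle mean).

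| v (assumed) | Reading of 60% | Vehicle mean | Treated mean | d | Power at 30 | Power at 36 |
|---|---|---|---|---|---|---|
| 10% | vs baseline | 2.79 | 1.24 | 0.620 | 66% | 74% |
| 20% | vs baseline | 2.48 | 1.24 | 0.496 | 47% | 55% |
| 10% | vs vehicle | 2.79 | 1.116 | 0.670 | 72% | 80% |
| 20% | vs vehicle | 2.48 | 0.992 | 0.595 | 62% | 70% |

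Only the first two rows keep the treated mean that 7.1 states.

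**The case against.** The strongest reply is that RBS is a leftover label that every reader will take as the corneal staining score, in a phase I/II trial of preliminary efficacy. Much of this stands. The documents do point to corneal fluorescein, and the conjunctival Lissamine score is a weak rival because it belongs to a secondary endpoint. Selection precedes randomization, both eyes are examined throughout (6.5), and 7.2 plans secondary analyses of the non-target eye. But the rule still does not name the score, and relabelling would not give the 3.1 and 2.5 a source on another scale.

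Some stronger readings are tempting but unsupported:

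- **Biased treatment comparison.** The target eye is chosen before assignment, so the missing score cannot favour an arm.
- **An underpowered trial.** Power for fluorescein could be above or below 80%. The vehicle improvements are assumptions, not figures from the plan.
- **A known rate of wrong-eye choices.** The documents give no between-eye correlation between dye scores and no tie rate, and with grades of 0 to 3 ties matter.
- **A vehicle response offset by the 80% reduction cited in 7.1.** An 80% active effect against 20% on vehicle restores the 1.86 difference, but it implies a treated mean of 0.62, not the stated 1.24. It is not a reading of the 60% assumption.

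The review also has limits: some pages and the scoring figures were not available, and the source of the RBS values is a citation that could not be seen. The firmest part is that RBS is absent from every listed visit.

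**Conclusion.** The point holds in two parts.

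**Target eye.** For subjects with both eyes eligible, the rule cannot be run as written. The result is an unreproducible choice of the eye carrying the primary analysis, not lost data. Subjects with one eligible eye, and endpoints measured per subject, are unaffected.

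**Power.** The sum in 7.1 is correct for RBS. For corneal fluorescein the 80% has no support in the documents. The zero vehicle response built into the inputs is a further weakness: under the assumed 10% to 20% improvement, power at 36 per arm runs from 74% to 55% with the stated treated mean, or from 80% to 70% if the 60% is relative to vehicle. These figures use RBS inputs and show sensitivity only; they are not estimates for fluorescein.

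Both parts need correcting, because one governs which eye is analysed and the other misattributes the stated power.

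**What to change.** 1. In the Study Summary and 7.2, replace RBS score with *screening corneal fluorescein score*. State how the five zone grades are combined, if the scoring figure in 3.3.1 does not already do so.
2. Keep 36 per arm. In 7.1, label 3.1 and 2.5 as RBS values. Then either restate power with a sourced fluorescein mean, SD and vehicle response, or state that 80% power corresponds to a between-arm difference of 0.67 SD with 36 evaluable per arm and 0.74 SD with 30. Enrolled is not evaluable: subjects leaving before week 8 are asked for week 10 procedures (4.4.2), and week 10 has no staining (6.5.7). Say whether the 60% is versus baseline or versus vehicle.
3. Minor wording: 7.1 attributes the 80% mean reduction to patients in the plural, while 1.4, with the same citation, describes one treated patient. Reconcile them.

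Optionally, the week 8 score could be adjusted for the Day 1 score already collected. No power gain is quoted, because 7.1 does not say whether 2.5 is the SD of the score or of its change.

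The cost is wording in three places, with no new patients, visits or tests. The downside is that the restated power may be less favourable.

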7.2 Statistical Methods

Biostatisticians from the Design and Analysis Core (DAC) of UIC-CCTS will perform the analysis. We will assess treatment efficacy based on the intent-to-treat principle using each participant's randomized treatment assignment to define treatment groups and outcomes. Safety variables will be analyzed with regard to treatment that participants actually received (the safety population). One eye (target eye) will be selected at screening visit for statistical comparisons as follows: (i) if only 1 eye meets inclusion criteria, this eye is used; (ii) if both eyes meet inclusion criteria, the eye with the higher RBS score is used; (iii) if both eyes have the same RBS score, then the one with the lower Schirmer I score is used; (iv) if both eyes have same scores, the right eye is used. Secondary analyses will be performed for the non-target eye as well. To assess the effect of treatment, we will compare each outcome measure between rhDNase I (study) vs. Vehicle (control) group over time using general linear mixed model, mixed-effects ordinal logistic regression, and mixed-effects multinomial logistic regression for continuous, ordinal and nominal variables respectively. Treatment, time and their interaction will be included in the model. Missing values of less than 25% will be imputed by using multiple imputations; otherwise will not be included in the analysis. Descriptive statistics will be utilized before the modeling to describe the sample. Assumptions behind each statistical method will be examined. Two-sided Pvalue less than 0.05 would be considered as statistical significance. All the analyses will be conducted by using SAS 9.2 (SAS Inst., Cary, NC).

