4.3 Subject Recruitment and Screening

Potential subjects will be recruited from the clinical practice of the investigator at the time of their routine eye examination visit. The clinical practice is located in the Illinois Eye and Ear Infirmary, Department of Ophthalmology and Visual Sciences, University of Illinois at Chicago (UIC). Subjects will include patients who have been diagnosed with oGVHD in the investigator's eye clinic (cornea clinic or the comprehensive eye clinic), in the Illinois Eye and Ear Infirmary. Patients diagnosed with oGVHD, and willing to enter the study, may be referred to the PI's clinic by other ophthalmologists at UIC, as well as the ophthalmology departments at Loyola University Chicago, University of Chicago, and Northwestern University. These centers will be provided with 'information sheets' to provide to subjects before they come to the PI's clinic. Although patients may be referred from these sites, no study procedures, including enrollment will be performed at any site, other than the PI's clinic in Illinois Eye and Ear Infirmary. All subjects will be will be screened, recruited, and will attend all study related visits only at the PI's clinic in Illinois Eye and Ear Infirmary.

Patients with definite ocular GVHD (with Schirmer I <10 and annoying or activity limiting visual symptoms) will be approached by a member of the research staff to determine if the subject might be interested in participating in a research study. If the subject is interested, the research staff member will describe the study. If the subject is willing to enter the study, the subject will be asked to review the study consent form, the PI will meet with the subject to review the form, the study will be discussed to confirm the subject's understanding of the study, and to answer any questions that the subject might have. Once the subject demonstrates understanding of the study and agrees to participate in the study, the subject will be asked to sign the informed consent form in the presence of the PI. Consent will be obtained prior to screening to determine eligibility. Screening procedures include documentation of definite oGVHD as well as other assessments as detailed in section 6.5.1. Eligible subjects will be enrolled in the study.

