Contact lenses, commonly used to treat oGVHD, will be withheld during the course of this study. This is necessary as the proposed primary efficacy outcome measure is corneal Fluorescein and Lissamine Dye Staining. Contact lenses can directly reduce corneal SPK and staining due to ensconcing and acting like a bandage that prevents corneal exposure to tear fluid inflammatory materials. Thus, because of over lapping effects on the primary outcome measure, it may not be possible to attribute any observed clinical benefit to rhDNase I treatment if contact lenses are used concurrently. This approach has been used in other clinical trials that have investigated the use of an anti-inflammatory agent in dry eye disease (NIH funded 'Dry Eye Evaluation and Management (DREAM) study').⁴¹

Stopping contact lens wear may increase the risk of worsening of oGVHD during the wash-out period and during the course of the study. However, because other eye drop treatments will continue during

the wash out period as well as during the course of the study, we do not expect any significant clinical worsening during the study. We do however expect the frequency of use of artificial tears to go up during the wash out period and during the course of the study.

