Subjects currently treating oGVHD with corticosteroids and/or Restasis will continue these treatments during the whole study. If patients are wearing contact lenses (Soft bandage contact lenses or PROSE lens), they will be asked to discontinue contact lens wear for 1 month prior to being enrolled (Baseline visit) and will be required to not wear contact lenses for the duration of the study (until week 10 visit). The study doctor will provide advice about decreasing oGVHD symptoms with artificial tears, eyelid massage, or warm compresses.

If the subject agrees to enter the study, the first treatment visit will be scheduled. If a washout period is needed, visit 2 will be after 2 weeks (±4 days). If a washout period is not necessary, visit 2 can be scheduled any time in the next 2 weeks after the screening visit.

6.5.2 Visit 2 Day 1 (Randomization and First treatment visit) Prior to first dose (Baseline)

- Vital Signs (blood pressure taken while subject is relaxed in a sitting position for at least 3 minutes, pulse, temperature, and height and weight (at this visit only).
- BSCVA (Snellen's chart)
- OSDI
- Schirmer 1 test and Fluorescein and Lissamine Dye staining
- Keratograph Oculus Redness Score
 - > Non-invasive Keratography Tear Film Break-up Time (NIKBUT)
 - > Tear Meniscus Height (TMH)
- TearLab Osmolarity Test
- InflammaDry Test for MMP-9 Protein
- Baseline Ophthalmic Examination (slit lamp examination, Ocular surface redness score)
- Tear fluid collection for analysis (PicoGreen, Cellometry)
- Physical Inspection of the Nose and Oropharynx
- Conjunctival and eyelid margin cultures
- Record changes in concomitant medication
- Adverse events since screening visit.

Randomization (by pharmacy)

Investigator/designee administers first dose

Post-Dose

RhDNase treatment for ocular GVHD Version: 10.0; 07-26-2018

Page 30 of 47

- Test Substance Tolerance (Visual Analogue Scale; VAS)
- Subjects will be trained on how to self-administer the study eye drops and be given a sufficient supply to last for 2 weeks to take home.
- Subjects will receive a study diary on which to record the day/time of each dose and any adverse effects.
- Post dose evaluation for any adverse effects.

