11.1 Records Retention

It is the investigator's responsibility to retain study essential documents. Research file documents will be uniformly held indefinitely after the closure of the research file per UIC IRB requirements.

12 Ethical Considerations

This study is to be conducted according to US and international standards of Good Clinical Practice (FDA Title 21 part 312 and International Conference on Harmonization guidelines), applicable government regulations and Institutional research policies and procedures.

This protocol and any amendments will be submitted to a properly constituted independent Institutional Review Board (IRB), in agreement with local legal prescriptions, for formal approval of the study conduct. The decision of the IRB concerning the conduct of the study will be made in writing to the investigator. The study may not commence until IRB approval is granted.

All subjects for this study will be provided a consent form describing this study and providing sufficient information for subjects to make an informed decision about their participation in this study. This consent form will be submitted with the protocol for review and approval by the IRB for the study. The formal consent of a subject, using the IRB-approved consent form, must be obtained before that subject undergoes any study procedure. The consent form must be signed by the subject or legally authorized representative, and the investigator-designated research professional obtaining the consent.

13 Study Finances

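### On the visit schedule, the analysed eye is chosen at screening, before the contact-lens washout, so in one-eye or unequal lens wearers the milder eye can be chosen for the primary analysis

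*Combined protocol and SAP*

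**What the plan says.** **Choice of eye.** The synopsis and Section 7.2 give the same rule: "One eye (target eye) will be selected at screening visit for statistical comparisons as follows". If only one eye meets the inclusion criteria, that eye is used. The next step is "ii) if both eyes meet inclusion criteria, the eye with the higher RBS score is used". Ties go to the lower Schirmer I, then to the right eye.

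**Lens effect.** Section 5.6 explains why lenses are withheld: "Contact lenses can directly reduce corneal SPK and staining due to ensconcing and acting like a bandage that prevents corneal exposure". It gives no size for the effect.

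**Washout timing.** Section 6.5.1, under the screening visit, says "If a washout period is needed, visit 2 will be after 2 weeks (±4 days"). Section 1.5 calls it a 14-day washout. Sections 4.2, 5.6 and 6.5.1 also ask wearers to stop lenses for 1 month before enrolment, which they equate with the baseline visit. The Section 6.5.1 heading places screening at Day -18 to 0.

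**Day 1.** The pre-dose list in Section 6.5.2 includes "Schirmer 1 test and Fluorescein and Lissamine Dye staining", with randomisation afterwards. Nothing in the document uses these readings to choose the eye.

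**The concern.** The protocol takes the lens effect seriously enough to remove it from the baseline and week 8 readings. On the visit schedule, however, the effect remains in the screening reading that ranks the two eyes. If a lens sits on the worse eye, it can lower that eye's score below the fellow eye's, and the rule then analyses the fellow eye. The lens eye becomes the non-target eye even if it is clearly worse on Day 1. If the lens takes that eye below an entry criterion, the first step of the rule hands the analysis to the fellow eye automatically.

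What is at stake is sensitivity. The primary comparison would include some eyes with less staining, and so less room for it to fall, in a trial with 36 subjects per group.

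**Working it through.** **1. The plan's own figure.** Section 7.1 gives mean 3.1, SD 2.5 and an expected mean of 1.24 on treatment, so the difference is 1.86. The test is a two-sided t test at 0.05 with 80% power. The normal approximation gives 2 × ((1.96 + 0.8416) × 2.5 / 1.86)² = 28.4, so 29 per group. Exact noncentral-t power is 79.5% at 29, 80.9% at 30 and 87.6% at 36. The stated 30 per group reproduces.

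**2. Timing.** When a washout is needed, screening to Visit 2 is 14 ± 4 days, that is 10 to 18 days. Take 1 month as 30 days.
- Lenses stopped at screening: 0 days off lens when the eye is chosen and 10 to 18 days at baseline, which is 30 - 18 = 12 to 30 - 10 = 20 days short of the 1-month rule.
- 1-month rule kept within the same gap: lenses have been off for 12 to 20 days when the eye is chosen.

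Both cannot describe the same subject. Either way, the eye is chosen before the washout is complete.

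**3. How often the milder eye is chosen (illustration).** Consider subjects with a lens in one eye only. Let D be the true score of the lens eye minus that of the fellow eye, D ~ N(µ, σ_D), with σ_D = 2.5 × √(2 × (1 - 0.6)) = 2.24. The SD of 2.5 is from Section 7.1. Assumptions: inter-eye correlation 0.6, µ of 0.5 to 2 points, and a lens effect s of 1 to 3 points. The milder eye is chosen when 0 < D < s:

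P = Φ((s - µ)/2.24) - Φ(-µ/2.24)

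For s = 2 and µ = 1, P = 0.673 - 0.327 = 0.345.

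**4. What that costs.** The mean baseline staining lost per one-eye wearer is L = E[D; 0 < D < s]. If a share q of subjects are one-eye wearers and the 60% effect is proportional, the detectable difference becomes 0.6 × (3.1 - qL). I assume q of 10% to 30% and leave the SD at 2.5. For s = 3, µ = 2 and q = 30%: 0.6 × (3.1 - 0.3 × 0.77) = 1.72, with power 82.2%.

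| s | P for µ = 0.5, 1, 2 | L for µ = 0.5, 1, 2 | Power at 36 per group |
|---|---|---|---|
| 1 | 0.18, 0.17, 0.14 | 0.09, 0.09, 0.07 | 87.0-87.4% |
| 2 | 0.34, 0.35, 0.31 | 0.33, 0.35, 0.33 | 85.3-86.9% |
| 3 | 0.46, 0.49, 0.49 | 0.62, 0.70, 0.77 | 82.2-86.2% |

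**5. A second model.** Step 3 allows negative scores, so I also used non-negative integer scores with mean 3.1 and SD 2.5, inter-eye correlation 0.5 to 0.9 and a proportional lens effect. Among one-eye wearers whose lens eye is truly worse, that eye is outranked in about 4-12% of cases for a 25% reduction and 23-46% for a 50% reduction. Further cases become ties, decided by Schirmer. If both eyes wear lenses with equal proportional reduction, the ranking never reverses, though ties become more common.

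**The case against.** **The eye may already be off lens at screening.** This is the best objection. Under the 1-month rule, lenses have been off for about 12 days or more by screening, and little of the lens effect may be left. Section 12 does not settle the order: it says consent "must be obtained before that subject undergoes any study procedure", but consent could come before both lens removal and the screening assessments. So a reader might infer that selection always precedes lens removal, and the documents do not establish that. They do contain a schedule on which it does, and no statement that selection is made off lens.

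**Bias.** A reader might infer a biased treatment comparison. That is not supported. The eye is chosen before randomisation, so the misselection is equal in expectation in both arms.

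**Eligibility.** A reader might also infer that lens wearers are screened out and the study population drifts. Entry is judged at screening (Section 4.3: "Consent will be obtained prior to screening to determine eligibility"), but the staining criterion is "Corneal/ conjunctival (Fluorescein and Lissamine Dye) staining ≥1", so conjunctival staining can satisfy it. Section 5.6 speaks of corneal staining only; it does not say that lenses lower Schirmer, conjunctival staining or OSDI. Screening out is a secondary possibility that cannot be quantified.

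**Who is affected.** Nothing in the protocol says that one-eye wear is common or that the lens is usually on the worse eye.

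**Recoverability.** Both eyes are treated and examined, Day 1 gives an off-lens baseline, and the non-target eye is analysed secondarily. This limits the damage but does not correct the primary analysis.

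**Conclusion.** The concern holds in a limited form. On the visit schedule, the primary-analysis eye is ranked on a reading that the protocol itself says a lens distorts, and the off-lens Day 1 reading is not used for that choice. Subjects with a lens in one eye or unequal wear can have the milder eye analysed. If the 1-month rule governs, the problem shrinks; the document does not say which rule governs.

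The consequence is a modest loss of sensitivity. In the illustration, power stays above the planned 80% even with a 3-point lens effect, which is almost the whole assumed mean of 3.1, and with 30% one-eye wearers. These results rest on an assumed inter-eye correlation, inter-eye difference, lens effect and share of wearers. The documents give none of these, so the table shows a range and not an estimate.

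**What to change.** 1. In the synopsis and Section 7.2, add that for subjects who stop contact lenses for the study, the target eye is selected by the existing rule from the Day 1 pre-dose (off-lens) staining and Schirmer readings, before randomisation. The screening-based rule stays for everyone else. This works whichever washout text prevails.
2. Reconcile the 1-month requirement (Sections 4.2, 5.6, 6.5.1) with the 14-day washout (Section 1.5), the 2-week interval to Visit 2 and the Day -18 to 0 screening window (Section 6.5.1). Which period applies is for the sponsor to decide.

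Eligibility stays as decided at screening; only the choice of eye moves.

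**Cost.** This is protocol wording, with no new measurement or visit. In lens wearers the eye would be chosen on the same reading that serves as baseline, which adds some regression to the mean. That is equal in expectation in both arms, so it affects the size of within-arm change and not the comparison.
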